7.3 STUDY OUTCOMES

- User engagement and retention in the program (number of app opens, number of days with at least one app open, number of weeks with at least one app open)
- Attitudes towards quitting: desire to quit, confidence to quit, difficulty to quit and self-efficacy
- Smoking behavior: quit attempts, change in cigarettes per day (CPD), smoking cessation via 7-and 30-day PPA (self-report and biochemically confirmed), continuous abstinence (self-report and biochemically confirmed), abstinence from all tobacco products, use of NRT
- Participant feedback on the set-up, use experience, design and impact of their assigned smoking cessation program

Outcomes include:

Primary:

- Total app opens in Pivot vs QuitGuide at 12 weeks (3 months)

Secondary:

- Change in expected difficulty in staying quit (participant self-report, scale 1-10) at 2, 4, 8, 12 weeks after enrollment
- Change in confidence levels towards quitting smoking (expected success in quitting, participant self-report, scale 1-10) at 2, 4, 8, 12 weeks after enrollment
- Desire to quit (yes/no) at 4 weeks after enrollment
- Self-reported abstinence (7-day and 30-day PPA) at 6, 8, 12, 26, 52 and 104 weeks after enrollment
- Self-reported abstinence (7-day PPA) at 2 and 4 weeks after enrollment
- Self-reported abstinence from all tobacco products at 6, 8, 12, 26, 52, and 104 weeks after

enrollment

- Biochemically confirmed abstinence at 12, 26, 52, and 104 weeks
 - To be considered biochemically abstinent:
 - Breath CO sample should be less than 10 ppm [16]
- Self-reported continuous abstinence at 26, 52 and 104 weeks, defined as a self-report of smoking no more than five cigarettes from 12 weeks after enrollment
 - 12 weeks is chosen because it allows for a full course of NRT, and it has been standard in studies that include pharmacotherapy for smoking cessation [17]
- Biochemically confirmed continuous abstinence at 26, 52, and 104 weeks, defined as a self-report of smoking no more than five cigarettes from 12 weeks after enrollment, and confirmation on all previous and present biovalidation tests:
 - Breath CO sample should be less than 10 ppm for participant to be considered abstinent [16]
- The proportion of participants who reduced their cigarettes per day (CPD) by $\geq 50\%$ compared to baseline at 4, 12, 26, 52 and 104 weeks

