7.5 PARTICIPANT RANDOMIZATION, STRATIFICATION AND ENROLLMENT

After signing the ICF, the participant will complete an online Baseline Questionnaire. Based on responses to the questionnaire, participants will be randomly assigned in a computer-generated 1:1 manner to either Pivot or QuitGuide using randomly permuted blocks of size 2 and 4, stratified by daily smoking frequency (≤ 14 vs ≥ 15 cigarettes per day), employment status (full-time or part-time employment vs unemployed), race/ethnicity (minority race/ethnicity vs non-Hispanic White), and expected difficulty staying quit (scale 1-10; self-reported score of ≤ 5 vs. ≥ 6). After randomization, participants will be emailed the link to access their assigned group. In both groups, participants will be able to access their assigned study app from the moment of randomization and beyond (ie, after the end of the 2-year study period).

Participants will be considered enrolled after completing the following 3 tasks: electronically signing the informed consent form, completing the Baseline Questionnaire and reporting the date they first logged in to their assigned app. If participants do not complete all three criteria, they may be removed from the study.

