7.7 SAMPLE SIZE AND JUSTIFICATION

As this is a pilot RCT and first assessment of Pivot compared to usual care, the study's sample size is powered to show differences in engagement, operationalized as the number of times participants open their assigned app. Previous clinical studies assessing Pivot have reported a mean of 24.2-38.7 app opens (SD range 20.8-25.9) by 90 days (data on file). In addition, Bricker et al. reported app opens comparing ACT-based smoking cessation apps (SmartQuit and iCanQuit) to QuitGuide. In one study, at 2-month follow-up, Bricker et al. reported mean (SD) app opens were 37.2 (46.1) for SmartQuit and 15.2 (13.6) for QuitGuide.[10] In a subsequent study, at 12-month follow-up, mean (SD) app opens were 37.5 (88.4) for iCanQuit and 9.9 (50.0) for QuitGuide.[11] Based on this data, we estimate mean (SD) 25 (25) app opens in the intervention arm vs. 15 (19) app opens in the control arm at 12 weeks. To detect a difference of 10 app opens or greater between Pivot and QuitGuide with 0.8 power and 0.05 alpha would require 156.7 participants, which we round up to 158. In a previous study, 272/319 (85.3%) participants completed the end-of-Pivot questionnaire at a mean (SD) 4.1 (1.4) months after enrollment. [13,14] Considering that we will assess our primary endpoint at 3 months (12 weeks), we are accordingly including an expected 15% attrition rate, with a plan to enroll up to 180 participants (up to 90 in each arm).

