11.2 ANALYSIS

In this pilot randomized control study, changes in measurements from baseline to intra-study to exit will be assessed. Participants will serve as their own controls and comparisons will be made to no change. One sample t-test will be used for numerical data. Fisher's Exact or Chi square tests will be used for categorical data. Analyses will be conducted to calculate mean (SD) for normally distributed variables for actual data or mean (SE) for modeled data and median (interquartile range) values in instances of non-normally distributed variables. McNemar test will be used for 2-category match-paired data. Cohen kappa statistic will be used for 3-category match-paired data. Statistical significance is set at $P < .05$. All deviations from the study protocol will be identified, recorded and analyzed.

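### Section 7.7 powers a between-arm difference in mean app opens, but the analysis rules in 11.2 do not produce that quantity

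*Combined protocol and SAP*

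**What the plan says.** The primary outcome in 7.3 compares total app opens between Pivot and QuitGuide at 12 weeks.

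Section 7.7 gives the planning values: "we estimate mean (SD) 25 (25) app opens in the intervention arm vs. 15 (19) app opens in the control arm at 12 weeks". The target is stated as "To detect a difference of 10 app opens or greater between Pivot and QuitGuide", and the result as "with 0.8 power and 0.05 alpha would require 156.7 participants, which we round up to 158". All the earlier data cited in support are means with SDs. Allocation under 7.5 is 1:1.

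Section 11.2 sets a different frame. Each participant is their own control, the reference is no change, and numerical data get a one-sample t-test. For description, 11.2 uses mean (SD) for normally distributed variables, mean (SE) for modeled data, and "median (interquartile range) values in instances of non-normally distributed variables". It makes no exception for the primary outcome, specifies no model for app opens, and names no between-arm test for any numerical variable. The synopsis agrees with this frame: its entry for performance endpoint and analysis is change from baseline.

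**The concern.** The plan defines its primary question and its sample size in terms of one quantity, the difference in mean app opens between arms. Its analysis section has no rule that yields this quantity.

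- **The named test does not fit the outcome.** Under 7.5 participants can use the assigned app from randomization, so a count of opens has no pre-randomization value to change from. A one-sample test within an arm could only ask whether its mean differs from zero, which says nothing about Pivot against QuitGuide.
- **The summary clause points away from the mean.** If app opens are skewed, as 7.7's own inputs imply, the clause calls for median and IQR.

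At stake are whether the 10-open difference is ever estimated, and whether the result can be set beside the earlier Pivot and QuitGuide means on which 7.7 relies. The primary effect measure and test also remain open until someone chooses them, possibly after seeing the data.

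**Working it through.** **Inputs (7.5 and 7.7).** Means 25 and 15, SDs 25 and 19, difference 10, power 0.80, alpha 0.05, allocation 1:1. Sidedness is not stated.

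**1. Which quantity was powered?**
- Pooled SD = sqrt((25² + 19²)/2) = sqrt(493) = 22.20, so d = 10/22.20 = 0.450.
- Normal approximation: n per arm = (625 + 361) × (1.960 + 0.842)²/10² = 77.4, total 154.8.
- Two-sample t-test, two-sided (noncentral t): 78.36 per arm, total 156.72. This matches the stated 156.7.
- The one-sided normal approximation gives 121.9, which does not match.
- At 79 per arm (158 in total), t-test power is 0.803.

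The 0.8 power therefore belongs to a two-sided comparison of two arm means.

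**2. Do 7.7's values imply non-normality?** App opens cannot be negative. Under a normal curve the share below zero would be:
- Pivot: Φ(−25/25) = Φ(−1.00) = 15.9%
- QuitGuide: Φ(−15/19) = Φ(−0.79) = 21.5%

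Both planning estimates imply right skew. The earlier figures in 7.7 are more mixed. QuitGuide at 2 months, 15.2 (13.6), has its SD below its mean, though Φ(−15.2/13.6) is still about 13%. QuitGuide at 12 months is 9.9 (50.0). The earlier Pivot means (24.2 to 38.7) and SDs (20.8 to 25.9) are given as ranges and not paired.

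**3. What would change if medians were reported?** The documents give no distributional shape, so three were assumed, each matched to 25 (25) and 15 (19). Welch power is from 10,000 simulated trials per row. The size 79 is 158/2, and 76 is about what remains per arm after 15% attrition from 180 (153/2 = 76.5).

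| Assumed shape | Population medians | Difference | Welch power, 76 per arm | Welch power, 79 per arm |
|---|---|---|---|---|
| Gamma | 17.3 and 8.1 | 9.2 | 0.80 | 0.82 |
| Negative binomial | 17 and 8 | 9 | 0.79 | 0.82 |
| Lognormal | 17.7 and 9.3 | 8.4 | 0.82 | 0.83 |

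The difference in medians is a different quantity from the powered 10, by a modest margin. Skew at this level does not undo the power of a comparison of means.

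**4. Setting 11.2 against 7.7.** Section 7.7 needs two arms, a difference in means and a two-sample test. Section 11.2 supplies a within-person comparison, a one-sample test and, for a skewed variable, a median. None of its stated rules gives the contrast in 7.7.

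**The case against.** The strongest reply is that the median clause concerns description only. It sets no estimand, effect measure or test, and a median and IQR for each arm can sit beside a test of means. Section 7.7 also shows plainly that a comparison of means was intended. All of this is correct, and it limits the point in four ways.

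- A reader might infer that the primary result will be medians. The documents do not say so. They leave the primary effect measure unstated, and the same sentence in 11.2 allows means for modeled data.
- A reader might infer that a rank test follows from the median clause. No rank test is named anywhere; the one test given for numerical data concerns a mean. Nor would a rank test lose power at 7.7's inputs: under the three assumed shapes it has about 0.92 to 0.99 at 76 to 79 per arm.
- A reader might see a switch triggered by the data. Section 11.2 describes no normality test and no switching procedure.
- Median and IQR is a conventional description of a skewed count, so preferring the mean is a choice and not the correction of an error.

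What the reply does not supply is the missing analysis. Intent in a sample-size section is not a prespecified primary analysis, and the analysis section describes a different kind of comparison.

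**Conclusion.** The point holds as a mismatch between 7.7 and 11.2. The trial is sized on a between-arm difference in mean app opens. Section 11.2, followed as written, tests within-person change for an outcome with no baseline and summarises skewed variables by medians. The missing between-arm analysis is the larger part; the median clause adds to the ambiguity.

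The mismatch does not weaken the sample size. The 156.7 reproduces exactly, and Welch power stays at about 0.79 to 0.83 under the assumed shapes. If medians alone were reported, the difference would be about 8.4 to 9.2 in place of 10, and it could not be compared with the earlier means. That skew is present follows from 7.7's planning values; the medians and simulated powers rest on assumed shapes. The plan should be corrected, but its design is not at fault.

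**What to change.** Add one sentence to 11.2: the primary analysis of total app opens at 12 weeks is the Pivot minus QuitGuide difference in arm means, with a 95% CI and a two-sided Welch test at the 0.05 level, whatever the distribution; a bootstrap CI is given as a check, and medians and IQRs for each arm are supplementary description. Confine the one-sample, own-control analysis to outcomes that have a baseline value.

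This needs no new data and no change in sample size. The downside is that a mean is sensitive to a few heavy users, which the supplementary medians would show. If the sponsor prefers another effect measure, 11.2 should name it and 7.7 should be recalculated for it.

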	
180 adult participants (up to 90 in each arm) who report daily smoking of 5 cigarettes or more. The study will be performed remotely on an ambulatory basis. Participants will be asked to setup and use their assigned program (Pivot for intervention or QuitGuide for control). Both study arms include the option for participants to order FDA-approved nicotine replacement therapy (NRT). The study duration is 104 weeks, with the estimated active time using the program of up to 6 months and the time thereafter as follow-up. Participants will receive online questionnaires at intervals throughout the study and may undergo up to 4 videocall biovalidation study visits in which they provide breath samples using a personal carbon monoxide (CO) breath sensor, which measures CO in exhaled breath.

Data Collection	Data will be collected through participant completion of emailed online questionnaires.
Performance Variables	
Comparison between the two smoking cessation programs on:
 
 • User engagement and retention in the program • Attitudes towards quitting: desire to quit, confidence to quit, self-efficacy and difficulty to stay quit • Smoking behavior: quit attempts, change in cigarettes per day (CPD), smoking cessation via 7-and 30-day PPA (self-report and biochemically confirmed), continuous abstinence (self-report and biochemically confirmed), abstinence from all tobacco products (self-report), use of NRT • Participant feedback on the set-up, use experience, design and impact on their assigned smoking cessation program, and use of other (non-study) smoking cessation tools
Performance Endpoint and Analysis	Change from baseline measurement

Contents

1.	List of Abbreviations	7
2.	Introduction.....	8
2.1	Background	8
2.2	Study Rationale	10
2.3	Potential Risks and Benefits.....	10
2.3.1	Known Potential Risks	10
2.3.2	Known Potential Benefits.....	11
2.3.3	Risk Benefit Assessment	11
3.	Objectives	11
4.	Definitions.....	12
5.	Control – QuitGuide Plus Nicotine Replacement Therapy.....	13
5.1	QuitGuide	13
5.2	Nicotine Replacement Therapy	13
6.	Intervention - Pivot	13
6.1	Pivot Breath Sensor	13
6.1.1	Indications for Use	14
6.2	Labeling and Packaging	14
6.3	Pivot Breath Sensor Submitting a Breath Sample (Specific Steps)	14
6.4	CO Log.....	15
6.5	Pivot App.....	16
6.6	Pivot Coaching	17
6.7	Pivot Nicotine Replacement Therapy (NRT).....	17
6.8	Pivot Moderated Online Community	17
7.	Study Design and Overview	17
7.1	Study Design	17

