9. DATA COLLECTION

Study personnel will collect information from the participant over the course of the study including:

- Age
- Gender
- Pregnancy status (self-reported) in women
- Race/ethnicity
- Employment status
- Education
- Type of smartphone participant uses (iPhone or Android)
- Number of years smoking
- Social and living environment relating to smoking
 - Live with other adults who smoke
 - Live with romantic partner who smokes
 - Number of close friends who smoke
- Alcohol use (AUDIT-C, 3 items)
- Screening for depressive symptoms (CES-D, 10 items)
- Quit attempts
 - Past 12 months
 - During the study
- Number of cigarettes currently smoked per day (CPD)
- 7-day point prevalence abstinence (PPA) (self-reported and biovalidated)
- 30-day point prevalence abstinence (PPA) (self-reported and biovalidated)
- Abstinence from all tobacco products (self-reported)
- Continuous abstinence (self-reported and biovalidated)
- Use of other tobacco products other than cigarettes including pipes, cigars, cigarillos, little filtered cigarettes, hookah, water pipe, any electronic cigarette product (e-cigs, vape, vapor), smokeless tobacco, chew, or snuff, and any other inhaled combustible material
- Use of smoking cessation medications past and present
- Use of other smoking cessation methods, past and present (for the present, methods other than those in the study program)
- Attitudes towards smoking
 - Desire to quit (y/n)
 - Confidence to quit (scale 1-10)
 - Perceived difficulty of staying quit (scale 1-10)
 - Self-efficacy
- Engagement
 - App opens (self-reported)
 - Number of days with app opens (self-reported)
 - Number of weeks with app opens (self-reported)
- Feedback on assigned program set-up and use
 - Ease/difficulty getting started
 - Use experience

- Design
- Impact on quitting
- Impact on staying quit
- How would you improve the experience of your assigned program?
- How likely are you to recommend your assigned program to a friend/colleague? (scale 1-10)
- How has using your assigned program affected the number of cigarettes you smoke per day? (increase, no change, decrease)
- Which of the following best describes your thoughts on your assigned program? ('nothing else can help me with smoking' to 'it will not help me with smoking')
- Which of the following best describes your assigned program's ability to help someone quit smoking? ('extremely helpful' to 'makes quitting smoking harder')

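### Section 11.2 assigns Cohen kappa, an agreement measure, to 3-category paired data although its stated comparison is with no change; the visible reach is small

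*Combined protocol and SAP*

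**What the plan says.** Section 11.2 opens with its purpose: "changes in measurements from baseline to intra-study to exit will be assessed". It then gives the reference for those comparisons: "Participants will serve as their own controls and comparisons will be made to no change". The synopsis row on performance endpoint and analysis agrees: "Change from baseline measurement".

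The section next matches methods to data types. For paired categorical data there are two rules, one after the other: "McNemar test will be used for 2-category match-paired data", then "Cohen kappa statistic will be used for 3-category match-paired data". The following sentence begins "Statistical significance is set at" and gives P<.05, with no exception for kappa.

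No separate purpose is stated for kappa, such as reliability or agreement between self-report and breath CO. No other method is named for paired data with three or more categories, and the items the kappa rule is meant to cover are not listed.

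One response set with exactly three levels is visible, among the feedback questions in Section 9: "How has using your assigned program affected the number of cigarettes you smoke per day? (increase, no change, decrease".

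**The concern.** McNemar and kappa are presented as the two-category and three-category versions of one analysis, but they address different hypotheses. McNemar's null is that the proportion in a category is the same at both times, which is the section's no-change comparison. The usual null for kappa is that the two answers agree no more often than chance. Rejecting it shows that people tend to give the same answer twice. It does not show that the distribution of answers moved, or in which direction.

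If a kappa P value below .05 were read as evidence of change, stable answers would count as change and a real shift could be missed. If kappa were only described, change in 3-category items would have no test at all.

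**Working it through.** **The plan's own figure.** The plan gives no sample size, power or data for a 3-category paired analysis. The only figure that can be reproduced is the sample size in Section 7.7, which rests on app opens: "we estimate mean (SD) 25 (25) app opens in the intervention arm vs. 15 (19) app opens in the control arm at 12 weeks". Common SD = √((25² + 19²)/2) = √493 = 22.20. A two-sided two-sample t-test with difference 10, alpha 0.05 and power 0.80 needs 78.36 per arm, or 156.72 in total. That matches the stated 156.7, and kappa plays no part in it.

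**Inputs for the check.** The tables below are assumed, because the documents contain no 3-category data. Rows are the first answer and columns the second. Each table has 90 pairs, one full arm in Section 7.7 before the 15% attrition assumed there (90 × 0.85 = 76.5).

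**Formulas.**
- Kappa = (p_o − p_e)/(1 − p_e), where p_o is the observed agreement and p_e = Σ r_i c_i is the chance agreement from row proportions r_i and column proportions c_i.
- Standard error under kappa = 0: √(p_e + p_e² − Σ r_i c_i (r_i + c_i)) / ((1 − p_e)√n).
- Stuart-Maxwell: χ² = d′S⁻¹d on 2 df. Here d holds the row total minus the column total for two of the three categories. S has diagonal entries (row total + column total − 2 × diagonal count) and off-diagonal entries −(n_ij + n_ji).
- Bowker: χ² = Σ (n_ij − n_ji)²/(n_ij + n_ji) over the three pairs of cells, on 3 df.

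**Table 1, no net change:** rows (20,5,5), (5,20,5), (5,5,20).
- Margins are 30/30/30 at both times.
- p_o = 60/90 = 0.667 and p_e = 0.333, so kappa = 0.333/0.667 = 0.50.
- Standard error = 0.0745, z = 6.71, P = 2×10⁻¹¹.
- d = (0, 0), so Stuart-Maxwell χ² = 0, P = 1.0.

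**Table 2, large shift:** rows (3,7,20), (3,7,20), (4,6,20).
- Margins move from 30/30/30 to 10/20/60.
- p_o = (3 + 7 + 20)/90 = 0.333 and p_e = (1/3)(10 + 20 + 60)/90 = 0.333, so kappa = 0.00, P = 1.0.
- d = (20, 10); S has diagonal 34 and 36 and off-diagonal −10, with determinant 34 × 36 − 100 = 1124.
- Stuart-Maxwell χ² = (36 × 400 + 2 × 10 × 20 × 10 + 34 × 100)/1124 = 21800/1124 = 19.4, P = 6×10⁻⁵.
- Bowker χ² = 16/10 + 256/24 + 196/26 = 19.8, P = 2×10⁻⁴.

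**Same kappa, different change.** Table 2 makes the second answer almost unrelated to the first, which is extreme for one person asked twice. Two further assumed tables keep ordinary within-person correlation. They use 79 pairs (158/2) and share the diagonal 22, 18, 15.

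| Table (rows) | Net change | Kappa | Kappa P | Stuart-Maxwell P |
|---|---|---|---|---|
| (22,4,4), (4,18,4), (4,4,15) | none | 0.54 | 1×10⁻¹¹ | 1.0 |
| (22,8,8), (0,18,8), (0,0,15) | every changer moves the same way | 0.56 | 5×10⁻¹⁴ | 2×10⁻⁵ |

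Kappa hardly separates them.

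**Simulation** (assumed probabilities, 79 pairs, 5,000 replicates, P<.05):
- No net change, true kappa 0.40: the kappa test rejects in 99.8% of replicates, Stuart-Maxwell in 4.5%.
- Distribution moving from 60/25/15% to 20/30/50% with independent answers: kappa rejects in 5.1%, Stuart-Maxwell in 100%.

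**Which outcomes are exposed.** The primary outcome in Section 7.3 is a count. Where the scale of a secondary outcome there is visible, it is a 1-10 score, a yes/no item, an abstinence or reduction proportion, a count or a multi-item instrument. None is shown with three categories at baseline and follow-up. The three-level Section 9 item asks what the program did to cigarette consumption, so it cannot be answered before the program starts.

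**The case against.** The best defence is that kappa may be meant descriptively. For an opinion item asked twice, agreement over time is a legitimate quantity. Section 11.2 states no hypothesis for kappa and never says its P value will be taken as evidence of change. The P<.05 sentence is general. This stands in part: a reversed conclusion needs the P value to be misread. However, the section's only stated comparison is with no change, and kappa sits beside McNemar as its three-category counterpart, so the text invites that reading. On the descriptive reading, 3-category change is left without a test.

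A reader might go further and infer that a listed change-from-baseline result will come out wrong, with the increase/no change/decrease item as the example. The documents do not support that. The item has no baseline value and already records change within one answer. It could be paired only between follow-up times, and Section 9 gives it no time points. The satisfaction outcome in Section 7.3 is timed at eight weeks of the study, but its listed components do not include this item. The schedule in Section 8.8 is redacted, so repeated or other 3-category items can be neither confirmed nor excluded.

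A reader might also infer that a new between-arm ordinal model is needed. That is a separate question: the defect here is within-person, and 11.2 already names Fisher's exact or chi-square for categorical data generally.

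**Conclusion.** The point holds as a minor correctness fix. The rule as written names a statistic that does not test the section's own comparison. In the assumed tables the kappa P value and a proper test of change point in opposite directions: P<.001 against 1.0 with no net change, and 1.0 against P<.001 with a large shift.

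Those sizes depend on the assumed tables and on the kappa P value being read as a test of change. That kappa targets agreement and not change depends on neither. Whether any reported result is affected depends on whether a 3-category item is asked at least twice, which the visible text does not establish.

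**What to change.** In Section 11.2, replace the kappa sentence with a paired test of change for any 3-category item: Stuart-Maxwell (equal margins) or Bowker (symmetry), or an ordinal paired method where the categories are ordered, since the first two ignore order. Name the items covered and the time points compared. Keep kappa only where agreement is the stated question, and then name the two measures being compared. If no 3-category item is measured twice, delete the rule.

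The cost is one sentence. Data collection and sample size do not change.

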- Number of quit attempts at 4, 12, 26, 52, and 104 weeks (defined as answering ≥ 1 to the following question: “Since you began the study, how many times have you tried to quit smoking where you've gone at least 1 day without smoking a cigarette, even a single puff?”).
- User satisfaction with the smoking cessation program (set-up and getting started with program, recommend to friend, program design, program was useful for quitting, program helped me quit, program helped me stay quit) at 2, 3, 4, 5, 12, 26, 52 and 104 weeks
- Engagement with program, collected weekly during the first 12 weeks after enrollment:
 - Number of times app opened (self-report)
 - Number of days in which app was opened (self-report)
 - Number of weeks in which app was opened (self-report)
- Participant changes in self-efficacy at 6, 12, 26 and 52 weeks
- Participant changes in self-reported health and wellbeing at 26 and 104 weeks
- Self-reported NRT use at 4, 8, 12, 26, 52 and 104 weeks
- Use of other smoking cessation tools (apps, counseling, non-study medications, etc.) at 12, 26, 52, and 104 weeks
- Alcohol use behavior at 12, 26 and 52 weeks (Alcohol Use Disorders Identification Test-Concise or AUDIT-C screening questionnaire, 3 items) [18-20]
- Presence of depressive symptoms screening at 12, 26, and 52 weeks (Center for Epidemiological Studies Depression Scale or CES-D screening questionnaire, 10 items) [11,21-23]
- Living and social environment relating to cigarette smoking at 12, 26 and 52 weeks (live with other adults who smoke, live with romantic partner who smokes, number of close friends who smoke)
- Adverse events at 26, 52 weeks

Eligibility Criteria

The study population comprises current smokers, 21 years of age and above, who own and

regularly use a smartphone and are ready to quit smoking in the next 30 days.

Inclusion Criteria

- 21+ years of age
- Current daily cigarette smokers (at least 5 cigarettes per day) for the past 12 months
- Plans to quit smoking in the next 30 days
- Resident of the United States
- Able to read and comprehend English
- Owns and uses a smartphone compatible with the study app (iPhone 5 and above with operating system iOS 12 and above, or, Android 7.0 and above with operating system Android 7.0 and above)
- Has daily internet access on smartphone
- Comfortable downloading and using smartphone apps
- Willing to sign the Informed Consent Form

Exclusion Criteria

- Pregnancy (self-reported)

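### Section 11.2 applies one unadjusted P < .05 rule to primary and secondary outcomes alike, names no main abstinence result and plans no between-arm interval estimate

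*Combined protocol and SAP*

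**What the plan says.** Section 7.3 (Study Outcomes) names one primary outcome, "Total app opens in Pivot vs QuitGuide at 12 weeks (3 months"), and section 7.7 sizes the trial on it alone. Section 7.3 then lists 21 secondary bullets, most at several visits and in no order of importance. Three examples:

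- one bullet that covers two PPA windows, "Self-reported abstinence (7-day and 30-day PPA) at 6, 8, 12, 26, 52 and 104 weeks after enrollment"
- a separate bullet for abstinence verified by a breath CO test, which reads "Biochemically confirmed abstinence at 12, 26, 52, and 104 weeks"
- satisfaction items, ending "program helped me stay quit) at 2, 3, 4, 5, 12, 26, 52 and 104 weeks"

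Section 11.2 (Analysis) gives one decision rule for all of this: "Statistical significance is set at $P < .05". The planned summaries are "mean (SD) for normally distributed variables for actual data or mean (SE) for modeled data and median (interquartile range) values". On what is compared with what, it says "Participants will serve as their own controls and comparisons will be made to no change". The Synopsis (Performance Variables) instead promises a "Comparison between the two smoking cessation programs on" engagement, attitudes, smoking behaviour and feedback.

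Section 11.2 shows no redaction marks. It contains no testing order, no key secondary outcome, no multiplicity rule, no statement that secondary P values are exploratory, and no confidence interval.

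**The concern.** Abstinence is the result that readers of a cessation trial will look for. Section 7.3 defines it in six ways: self-reported 7-day PPA, self-reported 30-day PPA, abstinence from all tobacco, biochemically confirmed abstinence, self-reported continuous abstinence and confirmed continuous abstinence. 7-day PPA alone is listed at eight visits. With one threshold and no ranking, any version at any visit could be called significant under the plan, and a reader could not check against the document which result was meant to carry weight.

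The second part of the problem is what the plan leaves out. A pilot of this size can usefully give the size of the abstinence difference between arms and how uncertain it is. Section 11.2 does not ask for either.

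**Working it through.** **The plan's own figure.** Section 7.7 assumes mean (SD) 25 (25) against 15 (19), power 0.8 and alpha 0.05. The pooled SD is sqrt((25² + 19²)/2) = 22.20. A two-sided two-sample t-test at a difference of 10 needs 78.36 per arm, or 156.7 in total, which is the plan's figure. So alpha 0.05 was allotted to one between-arm test of app opens.

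**Count of listed results (section 7.3), each outcome once per visit.**

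- Abstinence: 7-day and 30-day PPA at six visits, 2 × 6 = 12; 7-day PPA at weeks 2 and 4, 2; all tobacco, 6; confirmed, 4; self-reported continuous, 3; confirmed continuous, 3. Sum 30.
- Attitudes and self-efficacy: difficulty 4, confidence 4, desire 1, self-efficacy 4. Sum 13.
- Other smoking behaviour and treatment use: CPD reduction 5, quit attempts 5, NRT use 6, other tools 4. Sum 20.
- Satisfaction 8; engagement 3 (three measures, once each). Sum 11.
- Health and wellbeing 2, AUDIT-C 3, CES-D 3, living environment 3, adverse events 2. Sum 13.

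Total: 30 + 13 + 20 + 11 + 13 = 87. The last group is not in the Synopsis list of between-program comparisons; without it, 87 − 13 = 74.

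The count moves with the reading. It is 86 if the app-opens engagement measure is dropped as overlapping the primary. It is 91 (34 for abstinence) if confirmed abstinence covers both 7-day and 30-day PPA, as the Synopsis and section 9 suggest. It is 120 if the three engagement measures are tested in each of the 12 weeks.

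**Expected results below .05 if nothing differs**, at exact size 0.05. Expectations add whatever the correlation:

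- 0.05 × 87 = 4.35
- 0.05 × 74 = 3.7
- 0.05 × 30 = 1.5

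**Chance of at least one among the 30 abstinence results.** If independent, 1 − 0.95^30 = 78.5%. The documents give no correlations, so the other rows are assumptions (simulated two-sided z-tests with a common correlation, 100,000 draws):

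| Assumed correlation | Chance of at least one |
|---|---|
| 0 | 79% |
| 0.5 | 51% |
| 0.7 | 34% |
| 0.8 | 25% |
| 0.9 | 17% |

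Section 11.2 allows Fisher's exact or chi-square tests. At 90 per arm and rates of 10% to 30%, chi-square has true size of about 0.05 and Fisher's exact about 0.030 to 0.034. Choosing Fisher's test would lower all of these figures. At size 0.03, for example, the independent case is 1 − 0.97^30 = 60%, and the expected count is 0.03 × 30 = 0.9.

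**Precision that the plan would leave unreported.** The 95% half-width for a difference in proportions with 90 analysed per arm is 1.96 × sqrt(2p(1 − p)/90). At an assumed p = 0.15 this is 10.4 points, and at p = 0.35 it is 13.9 points. If 15% were lost, as section 7.7 allows, 76.5 per arm would remain and the same formula gives 11.3 and 15.1 points.

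**The case against.** The strongest reply is that this is a self-described pilot with one pre-specified, sized primary outcome. Secondary outcomes and visits are listed in advance, and section 11.3 commits the final report to the attitude and smoking-behaviour outcomes. Nothing invites selective reporting, and formal multiplicity control of secondary outcomes in a pilot is largely a matter of preference. Much of this stands. The primary outcome's error rate is untouched, and no formal adjustment is needed. But the plan nowhere links pilot status to how secondary P values are read; it sets a significance rule instead.

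Four stronger readings are tempting, and the documents do not support them.

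- *A false positive is near certain.* For all 87 results the independent figure is 98.8%, but independence is untenable. The same people are measured repeatedly, confirmed abstinence is a subset of self-reported abstinence, and confirmed continuous abstinence requires passing every earlier test. At a common correlation of 0.5 or 0.7 the figure for 87 is 75% or 48%. All of these also assume no true effect anywhere.
- *At least 87 tests are planned.* The 87 are listed results. No section says each will be tested, and some, such as adverse events, may only be described.
- *The count should be 133*, treating the six satisfaction and three living-environment items separately (87 + 5 × 8 + 2 × 3). This needs every satisfaction item at all eight visits. Section 7.3 does not say so, and the schedule in section 8.8 is redacted.
- *Section 11.2 plans arm-by-arm summaries and between-arm tests.* It mentions no arms. The only test named for numerical data is a one-sample t-test against no change, so the calculations above show what would happen if the rule were applied to between-arm tests.

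A reader could also say that reported counts or SEs would let anyone build an interval afterwards. That may be so, but it is not a planned estimate and does not settle which abstinence result is the main one.

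**Conclusion.** The point holds as a gap in wording that is cheap to close. It is not a threat to the primary result. What is certain from the text is that one unadjusted threshold is not limited to the primary outcome, that no abstinence definition or visit is singled out, and that no between-arm difference or interval is planned.

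The size of the problem depends on how many listed results are tested, which the plan leaves open. The expected counts (4.4 of 87, 3.7 of 74, 1.5 of 30) assume that all are tested at exact size 0.05 with no true effects, but need no assumption about correlation. The 79% for abstinence is the independent case. The 51% to 17% range rests on assumed correlations of 0.5 to 0.9, and even its lower end is more than three times the nominal 5%. Fisher's exact test would reduce these figures.

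**What to change.** In section 11.2:

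1. Reserve the claim of significance at P < .05 for the primary between-arm comparison of app opens at 12 weeks.
2. Report secondary outcomes as between-arm differences with 95% confidence intervals, and label any P value nominal.
3. Name one abstinence definition and visit in advance as the headline abstinence estimate, for example biochemically confirmed 7-day PPA at one stated visit. It need not be tested in sequence after app opens. Making an abstinence test depend on an engagement result is a debatable choice in a pilot, and estimation does not require it.

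The cost is a few sentences and a little more analysis work, with no extra participants or data. It is slightly more than a change of label, because between-arm intervals need a stated between-arm method and a rule for participants with missing abstinence data, and section 11.2 gives neither. The downside for the sponsor is that fewer secondary results may be called significant.
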